## Approach

**Overview:** The goal of this proposal is not to determine the efficacy of any specific intervention program but, rather, to capitalize on an intervention with proven efficacy as a tool to study the biological underpinnings of learning. Forty children with dyslexia will be recruited to participate the Lindamood-Bell *Seeing Stars* intervention, which combines training in phonological and orthographic processing (details can be found in our recent work and the published manual). Pilot data on 26 children with dyslexia demonstrate **highly significant** ( $p<10^{-10}$ ) changes in reading skills as indexed by the Woodcock Johnson Basic Reading Skills composite, with average improvements of 0.9 SD over 8 weeks (**Figure 1**). Reading automaticity (Test of Word Reading Efficiency (TOWRE)  $p<10^{-6}$ ) and Reading Fluency ( $p<10^{-5}$ ) also show highly significant change, confirming the generalizability of the intervention.

Each child will participate in six measurement sessions. Two sessions will occur prior to the intervention and will serve as a control period (individual baseline); one session will be conducted at the mid-point of the intervention; one immediately post-intervention; two long-term follow up sessions will be conducted at 6- and 12-months post-intervention. Multiple baseline sessions will allow each child to serve as their own control, and intervention-driven change will be compared to changes observed during the control period. For the aims of this proposal, multiple baseline sessions are preferable to a wait-list control group because it makes it possible to control for developmental effects within the same subjects that participate in the intervention. For example, given the focus on individual differences (**Aim 3**), it is important to consider each subject's baseline (pre-intervention) growth rate as a potential covariate for differences in growth during the intervention period. Additionally, two control groups (see below) will serve as a comparison for long-term intervention effects.

**Figure 1: Reading skills improve substantially and systematically over the course of the *Seeing Stars* intervention and are stable during the baseline period.**

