**Behavioral assessment:** The Woodcock Johnson IV (WJ, Basic Reading Skills and Reading Fluency), TOWRE-2, Gray Oral Reading Tests (GORT-5, Rate, Accuracy, Fluency, Comprehension), and the Test of Silent Reading Efficiency and Comprehension (TOSREC) will be used to assess reading automaticity, accuracy and comprehension at each session. Phonological awareness (PA), phonological memory (PM) and rapid naming (RN) will be assessed with the Comprehensive Test of Phonological Processing (CTOPP). An auditory phoneme categorization task will be used to gain additional insights into phonological processing. Additionally, parent questionnaires will be used to assess (1) home literacy environment, education history, and current education experience, and (2) ADHD symptoms using the Strengths and Weaknesses of ADHD-Symptoms and Normal-Behavior (SWAN) rating scale.

**Participants and experimental design:** Subjects will be recruited from the University of Washington Reading and Dyslexia Research Database, a subject pool run by the PI. On average, 125 subjects per year are recruited into the Database, and each subject receives an extensive battery of behavioral tests (including the WJ, TOWRE, CTOPP, and Wechsler Abbreviated Scales on Intelligence (WASI)), MRI screening, and practice at an MRI mock-scanner that includes training on holding still. Additionally, subjects fill out questionnaires on education history, home environment, socioeconomic status (SES) and ADHD symptoms. Although the aims of this proposal do not target the relationship between SES and response to intervention, obtaining this information will allow other researchers to explore this relationship when data are made public (e.g.). This well-characterized subject pool makes it possible to recruit matched samples of intervention and control subjects with specific behavioral and demographic characteristics. In our experience, there is very low subject attrition because all subjects have already visited the lab and are familiar with the research protocol.

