Intervention subjects (**N=40**) will be children between **nine and eleven years of age** who are below the 25th percentile in timed (TOWRE composite) **and** untimed (WJ Basic Reading Skills) single word decoding abilities, and within the normal range (+/- 1 SD) on measures of general cognitive abilities (WASI). Diagnosis of ADHD will be an exclusion criterion due to concerns over motion. Pilot measurements on children 7-12 years of age demonstrate that the intervention is equally effective ( $d \sim .9$ ) across this age range. By focusing on 9-11-year-old children less data will be lost due to motion and subjects will stay focused for longer scan sessions.

**Intervention protocol:** Intervention will be administered to participants in Lindamood-Bell learning centers in the Seattle area four hours a day, five days a week, for eight consecutive weeks during summer vacation. Trained tutors will work one-on-one with each child. Importantly, the scientific research will be completely independent of the administration of the intervention to eliminate any potential conflicts of interest. Lindamood-Bell will not have access to any information the PI's laboratory collects on the subjects, including subject attrition.

The Lindamood-Bell “*Seeing Stars*” instruction program teaches phonological and orthographic processing through a combination of mental imagery and sensory-motor learning. Children practice visualizing the orthography of words, starting from simple consonant-vowel syllables and systematically working into more complex consonant-vowel-consonant pairings. The instruction focuses on segmenting and blending strings of phonemes into words and visualizing the relationship between the articulatory elements, and their representation as visual symbols. Phonological awareness is systematically built through articulatory exercises where children are taught to attend to the relationship between motor movements of the mouth and tongue, and speech sounds in words, and the corresponding letters. As children build a stronger foundation of phonological and orthographic knowledge, additional practice with increasingly complex sight-word identification and phonological decoding is layered into the intervention.

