In the neuroimaging literature, convergent findings, across multiple labs, have identified tissue properties of the arcuate fasciculus and superior longitudinal fasciculus (SLF) as potential biomarkers for dyslexia by demonstrating that tissue properties: (a) correlate with pre-reading skills such as phonological awareness, (b) differentiate preschool children and infants at risk for dyslexia from not-at-risk individuals, (c) develop more rapidly in good versus poor reading children, and (d) predict future reading gains in elementary school children with poor reading skills. What is particularly noteworthy is that arcuate/SLF tissue properties predict future reading development better than any behavioral measure. **However, none of these studies have assessed whether tissue properties are predictive of behavioral gains in an intervention setting.** Assessing the predictive power of this biomarker in a controlled intervention setting is both important for ruling out the possibility that predictions were influenced by environmental differences among children, and for the practical purpose of developing tools to predict a child's likelihood of success before the substantial commitment involved in this popular intervention program. The successful development of a predictive model can then be extended to other intervention programs through our sharing of reproducible analysis tools.

**Figure 4: Arcuate diffusivity predicts reading improvement.** Examining the region of the arcuate identified by Wang and colleagues, we find that pre-intervention diffusion properties predict each child's rate of improvement on the TOWRE. Children with lower diffusivity showed greater RTI. Using a step-wise, multivariate regression model to compare arcuate diffusivity, PA, and RN as predictors of RTI, only arcuate diffusivity was retained as a significant predictor. In other words, this biomarker subsumes the predictive value of the most widely used behavioral predictors.

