**Innovation:** The concept of “neuroprognosis”, or using brain measurements to make useful and prognostic predictions, has generated a lot excitement, and a flurry of publications in the field of educational neuroscience (for review see). However, one of the limiting factors is that there is always substantial variability in the quality, and type, of education that children have access to. This sets an upper-bound on the potential accuracy of any prediction: even if the critical brain property is identified for a particular academic skill, a substantial portion of the variance in outcome measurements will be due to differences in a child’s environment. Indeed, roughly 50% of the variance in reading skills is the product of environmental factors. The current proposal benefits from an intervention design in which environmental factors are controlled across subjects, allowing us to test whether there are neuroanatomical factors, unique to the child, that predispose them to succeed in the intervention program. Our approach to prediction will begin by examining biomarkers that are motivated by the literature and pilot data. After establishing the predictive value of these theory-driven biomarkers, we will use **cutting-edge machine learning algorithms to investigate whether a multivariate, data-driven approach can improve prediction accuracy**. Our approach to neuroprognosis benefits from unique tools we have developed to quantify tissue properties in the individual, and leverages collaboration with machine learning experts to explore the high-dimensional space afforded by these data.

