### Research questions and preliminary data

**Aim 3.A: Tissue properties of the arcuate as a biomarker for response to intervention:** The aforementioned studies demonstrating that arcuate tissue properties are predictive of longitudinal growth employed the AFQ software package, which is developed by the PI’s lab. Hence, the proposed research team is optimally suited to follow up on these findings, develop methods for automated, brain-based predictions of reading outcomes, and disseminate these tools to the field. Wang and colleagues reported that a specific region of the arcuate is predictive of reading outcomes when children are followed longitudinally in a conventional school setting. Examining this same region of the arcuate, we find that **each subject’s pre-intervention diffusivity values predict their improvement during the intervention above and beyond baseline behavioral measures (Figure 4)**. These data are a promising example demonstrating that biomarkers identified in one laboratory, can be replicated and extended by another lab, and lend support to the perspective that anatomical properties of the arcuate play a role in determining how easily children learn reading skills. **Such an extension is made possible through open sharing of code, and is facilitated by the open science approach of the PI’s lab.** Pilot data clearly establishes the feasibility of predicting learning outcomes based on properties of the arcuate (power = 0.93 for RD; 0.99 for AD at  $\alpha = 0.05$ ). The critical question is whether this biomarker predicts long-term follow-up measurements (above and beyond variance predicted by baseline behavioral data), since long-term achievement is the ultimate goal of an intervention. This type of long-range, post intervention prediction has not been examined before in the neuroimaging literature. Cross validation will be used to test out of sample generalization and assess whether biologically specific qMRI parameters improve prediction accuracy.

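### Aim 3.A: the claim that the design controls the child's environment covers the eight-week programme, not the 6- and 12-month outcomes that the plan calls critical, and no environmental sensitivity model is named

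*Combined protocol and SAP*

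**What the plan says.** In the Research Strategy, the Aim 3 Innovation paragraph notes that "roughly 50% of the variance in reading skills is the product of environmental factors" and presents the design as the answer: "The current proposal benefits from an intervention design in which environmental factors are controlled across subjects". The Significance paragraph gives the purpose as "ruling out the possibility that predictions were influenced by environmental differences among children".

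The controlled element is described under Intervention protocol: one-on-one tutoring "four hours a day, five days a week, for eight consecutive weeks during summer vacation".

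Aim 3.A ranks the outcomes: "The critical question is whether this biomarker predicts long-term follow-up measurements (above and beyond variance predicted by baseline behavioral data". The Approach overview fixes the timing: "two long-term follow up sessions will be conducted at 6- and 12-months post-intervention".

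The Approach section also says which environmental data exist. Parent questionnaires cover home literacy, education history and current education, and SES is recorded at entry to the subject database. On SES it adds: "Although the aims of this proposal do not target the relationship between SES and response to intervention", and leaves that relationship to other users of the public data.

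Neither Aim 3.A, the machine-learning paragraph nor the Aim 3 power statement gives any of these variables a role. Two other covariates are mentioned elsewhere as possibilities: each child's pre-intervention growth rate (Approach overview) and details of delivery (Intervention fidelity and monitoring).

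**The concern.** The argument for environmental control rests on all children receiving the same instruction. That holds for the tutoring while it lasts. By 6 and 12 months the children have had a long interval in which the plan describes no control of schooling, extra tutoring or home support. That they go back to ordinary home and school life is an inference from the summer timing and the visit schedule, but a safe one.

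If arcuate diffusivity is associated with home circumstances, and those circumstances affect reading after the programme, the long-term slope could partly reflect environment. Baseline reading scores can carry past environmental influence. They cannot carry differences in support that arise later.

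Matching on SES does not help here. It applies to the control groups, while the Aim 3 regression is fitted within the 40 intervention children. At stake is the interpretation of a significant 12-month slope as a property of the child's neuroanatomy.

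**Working it through.** **1. Coverage of the control.** 4 hours × 5 days × 8 weeks = 160 hours, all before the post-intervention visit. The critical outcomes fall 6 and 12 months after that. No passage extends the control into this interval.

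**2. The plan's own power figure.** Statistical Design and Power gives 0.96 for left arcuate diffusivity with 40 children at α=0.05. It cannot be reproduced, because no correlation, R² or slope is given. Back-solving power = Φ(atanh(r)·√(n−3) − 1.96) for 0.96 at n=40 gives r≈0.54 (two-sided; sidedness is not stated). The pilot result in Aim 3 concerns improvement during the intervention, so no power is stated for the 6- and 12-month question.

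**3. False positives for a marker with no effect of its own.** Let a be the marker–environment correlation and b the environment–outcome correlation. Omitting environment produces an apparent correlation r = a·b. Rejection rate = Φ(q − 1.96) + Φ(−q − 1.96), with q = atanh(r)·√(n−3). I take n = 40 × 0.9 = 36; the 10% attrition is stated for Aim 1 only, so its use here is an assumption. All values of a and b are assumed.

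| a | b | r | q (√33 = 5.745) | Rejection rate |
|---|---|---|---|---|
| 0.2 | 0.1 | 0.02 | 0.115 | 5.2% |
| 0.4 | 0.2 | 0.08 | 0.461 | 7.5% |
| 0.2 | 0.3 | 0.06 | 0.345 | 6.4% |
| 0.4 | 0.3 | 0.12 | 0.693 | 10.7% |
| 0.4 | 0.5 | 0.20 | 1.165 | 21.4% |

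The first two rows represent the case in which baseline scores absorb most of the environmental effect, leaving only a small residual b. The last three use larger values of b, as if the baseline adjustment removed little.

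**4. Cost of adjustment.** Take r=0.54 and three covariates (SES, home literacy, and age if used), so that √(n−3) becomes √(n−6).

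- Covariates unrelated to marker and outcome: n=40, power 0.957 to 0.941; n=36, 0.935 to 0.911. That is 1.6 and 2.4 points.
- Covariates explaining 16% of marker variance (one correlation of 0.4, since 0.4² = 0.16) with no effect of their own on the outcome: f = 0.54·√0.84/√(1 − 0.54²) = 0.588; partial r = f/√(1+f²) = 0.507; power at n=40 = Φ(atanh(0.507)·√34 − 1.96) ≈ 0.90, against 0.957 unadjusted.

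The degrees of freedom used by the baseline behavioural covariates are common to both models and are ignored here. Covariates that explain outcome variance would recover some of the loss.

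**The case against.** The strongest reply is that the plan never says environment is controlled at 6–12 months. The Innovation sentence goes on to speak of succeeding in the programme, and the Significance paragraph speaks of a controlled intervention setting. That is right: a reader might infer a flat contradiction, and the text does not contain one. The gap appears when the same argument is relied on for the follow-up outcome, to which Aim 3.A gives priority without restating the limit.

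A reader might also infer that the plan refuses to adjust for SES. It does not. It says the aims do not target the SES–response relationship, which does not bar SES as a covariate. On home literacy and schooling it is silent. Covariates are contemplated elsewhere, and the Aim 3 analysis is to be preregistered, so the list is still open. This stands, and it is why the point is about prespecification.

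Third, baseline reading at ages 9–11 may already carry much of the home influence. This also stands, and it puts the low end of the range near 5%.

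Fourth, a purely predictive aim needs no confounder control. That is fair for the practical use of the marker. However, Aim 3 also seeks neuroanatomical factors belonging to the child, which is an explanatory claim. Reporting both slopes serves both purposes.

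Finally, age might be pressed as a confounder across the 9–11 range. The documents give little support: under Participants and experimental design, the intervention is reported as equally effective from 7 to 12 years. That evidence does not cover the follow-up period, so age can be an optional covariate but does not carry the point.

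**Conclusion.** The concern holds in a limited form. The environmental control invoked in Aim 3 covers the eight-week programme; the critical outcome lies 6 and 12 months beyond it; and no Aim 3 model names the SES, home-literacy or education data that are collected.

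The documents do not show that the arcuate prediction is confounded. The range of about 5% to 21% rests on assumed correlations and on n=36. Its upper end supposes that the planned baseline adjustment leaves an environment–outcome correlation of 0.5. It would also be wrong to treat the plan's 50% environmental share as the share for this outcome, because that figure concerns reading skill in general, not gain or follow-up status in this sample.

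The consequence is for what Aim 3 may conclude at 6 and 12 months. Aim 3 is not a listed trial outcome, but this is one of its main claims, and the remedy is cheap.

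**What to change.** In the preregistration of the Aim 3.A long-term regressions:

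1. Keep the planned model, adjusted for baseline behavioural data.
2. Add one prespecified sensitivity model with SES and the baseline home-literacy score as covariates, age optional. Report the arcuate slope and its confidence interval with and without them, at both 6 and 12 months.
3. Use post-programme education experience only if the parent questionnaire is repeated at follow-up. The plan does not say that it is, and it lists no item on reading help received between visits.
4. Limit the statement that environment is controlled or ruled out to the end-of-programme outcome.

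The cost is preregistration wording and two or three degrees of freedom; the baseline data are already planned. The adjusted model loses about 2 points of power if the covariates are unrelated to marker and outcome, and more if they correlate with the marker (about 0.90 instead of 0.957 at n=40 when they explain 16% of its variance). Because the planned model stays in place, that loss affects only the sensitivity analysis. With about 40 children the covariate list should stay this short.

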### Research questions and preliminary data

**Aim 3.A: Tissue properties of the arcuate as a biomarker for response to intervention:** The aforementioned studies demonstrating that arcuate tissue properties are predictive of longitudinal growth employed the AFQ software package, which is developed by the PI’s lab. Hence, the proposed research team is optimally suited to follow up on these findings, develop methods for automated, brain-based predictions of reading outcomes, and disseminate these tools to the field. Wang and colleagues reported that a specific region of the arcuate is predictive of reading outcomes when children are followed longitudinally in a conventional school setting. Examining this same region of the arcuate, we find that **each subject’s pre-intervention diffusivity values predict their improvement during the intervention above and beyond baseline behavioral measures (Figure 4)**. These data are a promising example demonstrating that biomarkers identified in one laboratory, can be replicated and extended by another lab, and lend support to the perspective that anatomical properties of the arcuate play a role in determining how easily children learn reading skills. **Such an extension is made possible through open sharing of code, and is facilitated by the open science approach of the PI’s lab.** Pilot data clearly establishes the feasibility of predicting learning outcomes based on properties of the arcuate (power = 0.93 for RD; 0.99 for AD at  $\alpha = 0.05$ ). The critical question is whether this biomarker predicts long-term follow-up measurements (above and beyond variance predicted by baseline behavioral data), since long-term achievement is the ultimate goal of an intervention. This type of long-range, post intervention prediction has not been examined before in the neuroimaging literature. Cross validation will be used to test out of sample generalization and assess whether biologically specific qMRI parameters improve prediction accuracy.

**Aim 3.B: Does the severity of neural processing deficits predict resistance to remediation?** Even though the Seeing Stars intervention produces highly significant changes in reading skills, there is variability among children, with some children increasing by more than 2 standard deviations, and others showing limited growth. Is variability in response to intervention linked to the severity of underlying neural deficits? We will focus on three regions implicated in dyslexia: the temporoparietal region involved in phonological processing, the ventral occipitotemporal VWFA, and the inferior frontal region that has been proposed as a compensatory mechanism in dyslexia. The pre-intervention response profile in each of these regions will be used to index the magnitude of neural deficits in each subject and will be examined as a predictor of RTI. **Aim 3.B** is considered an exploratory analysis due to lack of supporting pilot data. However, the data for **Aim 3.B** will already be collected for **Aim 2**, and it is of theoretical importance to know whether more severe neural deficits, in specific components of the reading circuitry, are resistant to remediation.

